7.1.6. End-of-Study/Early Termination Assessments and Procedures

At the completion of the single- or multiple-dose phases, EOS/ET assessments and procedures will occur at 24 or 48 hours after initial study drug administration or upon early discontinuation. Each subject will be required to complete all EOS/ET assessments and procedures unless consent/assent, as applicable, has/have been withdrawn. End-of-study assessments will include:

- Collecting AEs/SAEs: all AEs/SAEs that occur during the Screening Phase and thereafter that started after Informed Consent/Assent, as applicable, has/have been signed.
- Performing physical examination: a comprehensive physical examination, excluding height and weight, to assess the subject's overall health and physical status. Record only abnormalities observed during the examination.
- Measuring vital signs: temperature, heart rate (beats per minute), respiratory rate (breaths per minute), and blood pressure (systolic and diastolic blood pressure, mmHg).
- Collecting a blood sample for pharmacokinetic assessments
- Collecting a blood sample for clinical laboratory tests: clinical laboratory tests as part of SOC will be acceptable.
 - Chemistry panels may include analysis of the analytes listed in section 12.5.3.
 - Hematology panels may include analysis of the analytes listed in section 12.5.4.
- Assessing respiratory and neurological function (see sections 12.2 and 12.3 and Appendix A). Assessments must be made by the Investigator, or designee.
- Updating and recording concomitant medications (including rescue medications).
- Assessing and recording current pain intensity (prior to giving rescue or further analgesics according to SOC) using an age-appropriate pain assessment instrument (FPS-R for ages 6 to ≤12; FLACC for ages 2 to <6 [see Appendix C and Appendix D, respectively]).
- Converting subjects to a discharge marketed opioid, if required.
- Scheduling the 14-day follow-up telephone call: assessment to include ongoing or new AEs, SAEs, and associated concomitant medications.

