NOTE: Within each age group, dose assignment will begin at lowest single dose and will proceed to the next dose after completion of all subjects. During the Single-Dose Phase, if rescue is needed, all study procedures (including PK) will continue except collection of pain scores. PK will only be discontinued if rescue is via oxycodone or oxymorphone. Within each age group, the Multiple-Dose Phase may proceed after IDMC assessment of the Single-Dose Phase data and selection by the IDMC of the treatment cohort doses that will be used in the Multiple-Dose Phase.

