Record Surgical Details ^k		X													
Record food consumption ^l		X	Monitored Throughout Study												
Rescue medication ^m			As Needed Throughout Study												
Convert subject to discharge opioid of Investigator's choice													X		
Schedule 14-day follow-up call with site													X		
Study Completion															X

FOOTNOTES:

Abbreviations: BL=Baseline; EOS=End-of-Study; ET=Early Termination; IRB=Institutional Review Board; PK=Pharmacokinetic; Pre-Op=Preoperative; Intra-op=Intraoperative

- ^a Tests results must be available for assessment by the Investigator, or designee, prior to dosing a subject.
- ^b Investigator, or designee, will train/retrain subjects, parent(s)/legal guardian(s) on the proper use and completion of the pain assessments.
- ^c Investigator, or designee, will assess if the subject has the cognitive ability to correctly complete the required pain assessments.
- ^d Pregnancy test (for females of child-bearing potential only) must be completed and the result assessed prior to administration of study drug. Serum β hCG at screening; urine pregnancy test before study drug administration, except if screening occurs in hospital.
- ^e Blood sample drawn before dosing study drug.
- ^f Clinical labs drawn as part of the SOC will be acceptable for study purposes. Intraoperative labs are acceptable provided they are drawn prior to first surgical incision and assessed by the Investigator prior to administration of the first dose of study drug.
- ^g Captured following execution of informed consent/assent.
- ^h Collected by the Investigator for up to 14 days after the last dose of study drug (**documented telephone follow-up required**).
- ⁱ See [Appendix B](#) and section 9.3 for concomitant medication reporting.
- ^j A pain assessment will also be completed at the time of rescue immediately prior to rescue medication administration. **No pain assessments will be completed beyond rescue.**
- ^k Must include type of procedure(s), date of procedure(s), surgical start/stop time, and anesthesia/analgesia start and stop time.
- ^l Record all times that any food was consumed and what food was consumed (Diet-as-tolerated [DAT], DAT-soft, Full Fluids, Clear Fluids, water) by the subject from 1h prior to dosing through to EOS at 24h post 1st dose/ET

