7.1.4. Single-Dose Phase Assessments and Procedures

The following assessments and procedures will be performed during the Single-Dose Phase (see [Table 3](#)) after the baseline assessments have been completed and the subject is dosed. Every effort should be made to collect blood samples at the assigned time intervals relative to the time of administration of study drug:

- Assess and record current pain intensity at 15 and 30 minutes and at 1, 1.5, 2, 4, 6, 8, 12, and 24 hours (or upon ET) after administration of study drug or until the subject requires rescue medication. Assessments must be made by the Investigator, or designee. Pain will be assessed at time of rescue, but no pain assessments will be completed beyond administration of rescue medication.
- Measurement of vital signs at 15 and 30 minutes and at 1, 1.5, 2, 4, 6, 8, 12, and 24 hours (or upon ET) after administration of study drug.
- Assess respiratory (see section [12.2](#)) and neurological function (see section [12.3](#) and [Appendix A](#)) at 15 and 30 minutes and at 1, 1.5, 2, 4, 6, 8, 12, and 24 hours (or upon ET) after administration of study drug. Assessments must be made by the Investigator, or designee.
- Collection of blood samples for pharmacokinetic assessments at 15 and 30 minutes and at 1, 1.5, 2, 4, 6, 8, 12, and 24 hours (or upon ET) after administration of study drug.
- Record food consumption: capture the date and time of each consumption of food as well as what was consumed eg, DAT, DAT-soft, FFs, CFs, water from 1 hour prior to first dose of study drug administration through EOS/ET.
- Record rescue medication: provide rescue medication on an as needed basis for breakthrough pain (BTP). Rescue medication may include opioid-based patient controlled analgesia (PCA) rescue (but must NOT contain oxycodone or oxymorphone) for as long as the PCA device remains in place per SOC. Oral rescue medications will also be allowed during the study, but also must NOT contain oxycodone or oxymorphone.
- Monitor and document AEs/SAEs throughout the study.
- Update and record concomitant medications (including rescue medications).

Subjects will complete the Single-Dose Phase when they complete the EOS assessments and procedures at 24 hours (or upon ET) following initial study drug administration.

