8.3. Subject Withdrawal Criteria

Subjects may be discontinued from the study for the following reasons, but not limited to, if deemed appropriate, by the Sponsor or Investigator:

- Subject enters the study in violation of the protocol
- Protocol deviation during the conduct of the study
- Subject (or subject's parent/legal guardian as age appropriate) withdraws consent (reason[s] for the study withdrawal must be specified)
- If, in the Investigator's opinion, it is not in the subject's best interest to continue (reason[s] for study withdrawal must be specified)
- Lack of analgesic effect
- Adverse event
- Pregnancy
- Use of an opioid antagonist (eg, naloxone)

- Other reasons (reason must be specified, for example, the subject moved, Investigator decision, Sponsor decision to terminate trial)

When a subject is “lost to follow-up” (ie, fails to return for study visits), a reasonable effort, comprised of no less than 3 documented phone calls on separate occasions and a certified mail letter, should be made to contact the subject’s parent(s)/legal guardian(s) to determine a reason for the failure to return. If, following these actions, the subject fails to be contacted or fails to return to the clinic, the subject should be identified as “lost to follow-up” in the eCRF.

The date a subject discontinues and the reason for discontinuation will be documented in the source and entered into the eCRF. If a subject discontinues from the study (regardless of the cause), all EOS/ET assessments and procedures should be completed. If, however, a subject withdraws consent, no EOS/ET assessments or procedures will be required except for the collection of AE information. This information should be recorded in the source document and entered into the eCRF.

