13.4. Effectiveness Analysis

The pain intensity difference (PID) at each post dose time point will be calculated as the pain intensity score at baseline minus the current pain intensity score at each post dose time point. Summary statistics of the pain intensity scores at each time point and PID at each post dose time point will be presented by pain assessment instrument, age group, treatment cohort, and study phase. For each subject, the PID over time will be transformed into a summary measure by calculating area under curve of PID (AUC_E) using the trapezoidal formula, adjusted for study duration. All time points before the first rescue medication will be used to calculate AUC_E . AUC_E will be analyzed by a heterogeneous analysis of variance (ANOVA) model with fixed effects for age group, treatment cohort, and the interaction of age group by treatment cohort for each study phase. The potential heterogeneity between the age-specific measurements will be assessed using a dummy variable for the difference in the statistical model. Least squared means of AUC_E for each combination of age groups and treatment cohorts and the corresponding 2-sided 95% CIs will be calculated based on the model.

Numbers and percentages of subjects who need rescue medication will be calculated by age group, treatment cohort, and study phase.

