13.7. Handling of Missing Data

All observed demographic, effectiveness and safety data will be used in the analyses. No data imputation will be performed other than for the pharmacokinetic plasma concentrations described in section [13.6](#).

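### Section 7.1.6 requires an end-of-study pain score that the rescue passages forbid, and section 13.4 does not say whether such a score enters the time-point summaries

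*Combined protocol and SAP*

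**What the plan says.** **Passages that require an EOS/ET pain score.**
- Section 7.1.6: "Each subject will be required to complete all EOS/ET assessments and procedures unless consent/assent, as applicable, has/have been withdrawn". One listed item is "Assessing and recording current pain intensity (prior to giving rescue or further analgesics according to SOC) using an age-appropriate pain assessment instrument".
- Section 7.1, in the text before Table 3, gives the same duty with the same single exception.
- Section 8.3 extends it to subjects who leave early: "If a subject discontinues from the study (regardless of the cause), all EOS/ET assessments and procedures should be completed". It then makes an exception for withdrawn consent.

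**Passages that stop pain scoring at rescue.**
- Table 3 footnote j and Table 4 footnote k: "No pain assessments will be completed beyond rescue".
- Section 7.1.4: "Pain will be assessed at time of rescue, but no pain assessments will be completed beyond administration of rescue medication". Section 7.1.5 repeats this for the Multiple-Dose Phase.
- Section 11.1 drops the remaining scheduled scores once rescue is given.
- The note to Figure 1 says that for a rescued Single-Dose subject "all study procedures (including PK) will continue except collection of pain scores".

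**Analysis.**
- Section 13.4: "Summary statistics of the pain intensity scores at each time point and PID at each post dose time point will be presented", with no reference to rescue. Later in the same paragraph AUC_E, and only AUC_E, is limited to time points before the first rescue medication. The Synopsis reads the same way.
- Section 13.7: "All observed demographic, effectiveness and safety data will be used in the analyses".

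**The concern.** A site has two instructions for the same child at the same visit. A child rescued at 4 h remains in the Single-Dose Phase to 24 h. Section 7.1.6 asks for a pain score then, and footnote j forbids it. With about 20 centres, both readings could occur within one cell.

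The analysis text does not resolve the conflict afterwards. A programmer working from 13.4 and 13.7 would include any EOS/ET score that was recorded, whether or not it followed rescue. The 24 h or 48 h row could then combine children on study drug alone with children who have had rescue medication, and nothing in the table would show it.

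This deserves attention because effectiveness is part of the primary objective, there is no control arm, each cell has 6 children, and the Independent Data Monitoring Committee (IDMC) reviews individual and aggregate effectiveness data before each escalation (section 7).

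**Working it through.** The plan states no figure on this point, so there is none to reproduce. The check compares the passages and then asks what each reading does to one table cell.

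1. **Does a rescued child reach the EOS visit?** Yes in the Single-Dose Phase: the Figure 1 note keeps the child in all procedures other than pain scoring. In the Multiple-Dose Phase section 7 links rescue for inadequate relief with discontinuation, and section 8.3 then calls for the ET assessments. An ET score taken just before rescue satisfies both sets of passages. One taken after rescue does not.

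2. **Does the parenthesis in the 7.1.6 pain item settle it?** No. It puts the score ahead of any analgesic given at that visit. It does not exempt a child rescued hours earlier.

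3. **Does the analysis text exclude a post-rescue score?** Only for AUC_E. The time-point summaries carry no limit, and 13.7 works towards inclusion.

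4. **What changes in a cell?** Take 6 children (section 13.1), all with complete data apart from the rescue rule. Let r be the number rescued before the EOS visit, *a* the mean PID of the unrescued children, and *c* the mean PID of the rescued children after rescue.
   - Section 7.1.6 followed: mean = [(6 − r)a + rc]/6, with n = 6.
   - Rescue passages followed: mean = a, with n = 6 − r.
   - Difference = [(6 − r)a + rc]/6 − a = r(c − a)/6.
   - Sites divided between the readings: n lies between 6 − r and 6.

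5. **Size and direction.** The documents give no value for r, a or c. The sign is that of c − a. Rescued children may score better because rescue worked, or worse because they were in more pain to begin with. No direction can be derived.

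6. **Is the unrescued group a clean comparator at 24 h?** Not fully. Section 9.3 permits standard-of-care (SOC) analgesia other than oxycodone or oxymorphone after the 12-hour assessment period in the Single-Dose Phase, even without rescue. An unrescued 24 h score may therefore also reflect another analgesic.

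**The case against.** The strongest reply is that the specific rule governs the general one. The ban is repeated in six places and printed in bold in both schedule tables. Sections 7.1.4 and 11.1 name the 24 h or ET score in the same item that ends scoring at rescue, and the Figure 1 note addresses the rescued Single-Dose child directly. On this view 7.1.6 is a checklist to be read alongside the ban. If sites do so, no post-rescue score exists and the silence of 13.4 does no harm.

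The reach is also narrow. AUC_E, the only modelled effectiveness measure, excludes post-rescue scores. The Synopsis describes Single-Dose effectiveness over 12 hours, so the 24 h score lies outside that window. Rescue counts are tabulated by age group, cohort and phase.

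Most of this stands, and it limits the point to a minor one. It does not remove it. Sections 7.1, 7.1.6 and 8.3 name withdrawn consent as the only exception, sections 7.1.4 and 11.1 still schedule a 24 h score, and 13.4 still summarises every time point.

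A reader might infer that post-rescue scores would flatter the dose cohort with the most rescue, or the least effective dose. The documents do not support this: they give no rescue rates or post-rescue scores, and the shift can go either way. Nor should the effect be attributed to a rescue opioid. Section 7.1.4 says rescue may include opioid patient-controlled analgesia and also allows oral rescue without requiring that it be an opioid.

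**Conclusion.** The point holds as a minor reconciliation. The EOS/ET passages and the rescue passages contradict each other on the pain score of an already rescued subject, and 13.4 with 13.7 would admit such a score to the descriptive pain and PID summaries if it were recorded.

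The consequence depends on at least one site following 7.1.6 literally. It is confined to the EOS/ET summaries (24 h, 48 h or early termination), where it alters both the mean and n in cells of 6. Neither size nor direction can be stated from the documents. It would be wrong to conclude that AUC_E is contaminated by post-rescue scores, because 13.4 excludes them.

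**What to change.** - **Sections 7.1, 7.1.6 and 8.3:** reconcile with the Figure 1 note, Table 3 footnote j, Table 4 footnote k and sections 7.1.4, 7.1.5 and 11.1. State that an EOS/ET pain score from a subject already rescued is either not taken, or taken and flagged as post-rescue. No treatment or rescue rule needs to change.
- **Section 13.4 and the Synopsis:** state that time-point summaries of pain intensity and PID use only scores before first rescue, as AUC_E does. Show n and the number already rescued at each time point. List any post-rescue scores separately.
- **24 h scores in unrescued Single-Dose subjects:** flag those taken after SOC analgesia permitted by section 9.3.

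**Cost.** A sentence in each place and flags derived from medication times, which section 9.3 already has recorded. Late rows will have smaller n and will describe a selected group, the children who did not need rescue. The table should say so, because that group may look better than the whole cohort.

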7.1.7. Follow-Up Telephone Call

A documented follow-up telephone call will be required 14 days after the last dose of study drug. Site staff will collect information regarding new AEs (including SAEs) or resolution of ongoing AEs/SAEs, including concomitant medications being used to treat any SAE or ongoing AE and any new analgesic medications started after Visit 2 (EOS/ET).

The date of discharge from the study will be recorded by the Investigator on the Completion/Discontinuation source document and eCRF page and will be the official EOS/ET for each subject. Study participation will end with the completion of the 14-day follow-up telephone call.

7.1.8. Throughout the Study - Adverse Events and Serious Adverse Events

- Any AE will be treated by the Investigator according to standard institution medical practices and guidelines.
- All AEs will be followed-up by the Investigator through 14 days after the last dose of study drug or until resolution, whichever comes first. SAEs will be followed until resolution, stabilization or until follow-up is no longer possible. The 14-day follow-up will occur by telephone and will be documented in the source record. Results of all follow-up blood analyses and medical, pharmacological, and non-pharmacological interventions must be documented by the Investigator in the source documents and on the appropriate pages of the eCRF.

8. SELECTION AND WITHDRAWAL OF SUBJECTS

8.1. Subject Inclusion Criteria

1. Males or females between 2 to ≤ 12 years of age. Females of child-bearing potential must be practicing abstinence or using a medically acceptable form of contraception (eg, intrauterine device, hormonal birth control, or double barrier method). For the purpose of this study, all peri- and post-pubertal females will be considered to be of child-bearing potential unless they are biologically sterile or surgically sterile for more than 1 year
2. Subjects must be at least 10 kg and BMI ≤ 30 .
3. Scheduled to have a surgery for which oral opioid analgesia will be needed to manage post-operative pain for at least 24 hours (Single-Dose Phase) or 48 hours (Multiple-Dose Phase) following intraoperative and/or postoperative parenteral analgesia
4. Be hospital inpatients, expected to be hospitalized for at least 24 hours (Single-Dose Phase) and 48 hours (Multiple-Dose Phase) following the initial administration of oxymorphone immediate-release
5. Lab samples, either drawn intraoperatively (prior to surgical incision) or from within 21 days preoperatively, for clinical chemistry and hematology laboratory analytes (the results must have been reviewed by the Investigator prior to study drug administration for study eligibility)
6. Able to provide pain assessment evaluations using an age-appropriate instrument provided in the protocol
7. On an intravenous analgesic regimen utilizing a short-acting opioid analgesic following surgery AND anticipated to be switched to an oral opioid as part of the analgesic regimen (according to institution SOC)
8. Demonstrated the ability to tolerate clear fluids following surgery according to the SOC at each institution
9. Informed of the nature of the study and written informed consent has been obtained from the legally responsible parent(s)/legal guardian(s)
10. Provided assent in accordance with IRB requirements
11. Line in place for blood sampling

8.2. Subject Exclusion Criteria

1. Known allergies or sensitivities to oxymorphone or other opioid analgesics
2. Known sensitivity to any component of the study drug
3. Life expectancy < 4 weeks
4. Positive pregnancy test at screening (females of reproductive age only)

5. Pregnant and/or lactating
6. Cyanotic heart disease
7. Respiratory, hepatic, renal, neurological, psychological disease, or any other clinically significant condition that would, in the Investigator's opinion, preclude participation in the study
8. Preoperative opioids administered for a period of more than 72 hours in duration
9. Abdominal trauma that would interfere with absorption of study drug
10. Increased intracranial pressure
11. Respiratory condition requiring intubation
12. History of uncontrolled seizures that are not being managed with anti-convulsants
13. Significant prior history of substance abuse or alcohol abuse
14. Received any investigational medication within 30 days prior to the first dose of study drug, or are scheduled to receive an investigational drug other than oxymorphone HCl immediate-release oral liquid during the course of the study
15. Received a monoamine oxidase inhibitor (MAOI) within 14 days prior to the start of study drug
16. Received oxycodone or oxymorphone within 48 hours prior to study start
17. Investigator anticipates that the subject and/or parent(s)/legal guardian(s) would be unable to comply with the protocol
18. Subject (and/or parent[s]/legal guardian[s]) is(are) unable to communicate effectively with study personnel at an age-appropriate level

8.3. Subject Withdrawal Criteria

Subjects may be discontinued from the study for the following reasons, but not limited to, if deemed appropriate, by the Sponsor or Investigator:

- Subject enters the study in violation of the protocol
- Protocol deviation during the conduct of the study
- Subject (or subject's parent/legal guardian as age appropriate) withdraws consent (reason[s] for the study withdrawal must be specified)
- If, in the Investigator's opinion, it is not in the subject's best interest to continue (reason[s] for study withdrawal must be specified)
- Lack of analgesic effect
- Adverse event
- Pregnancy
- Use of an opioid antagonist (eg, naloxone)

- Other reasons (reason must be specified, for example, the subject moved, Investigator decision, Sponsor decision to terminate trial)

When a subject is “lost to follow-up” (ie, fails to return for study visits), a reasonable effort, comprised of no less than 3 documented phone calls on separate occasions and a certified mail letter, should be made to contact the subject’s parent(s)/legal guardian(s) to determine a reason for the failure to return. If, following these actions, the subject fails to be contacted or fails to return to the clinic, the subject should be identified as “lost to follow-up” in the eCRF.

The date a subject discontinues and the reason for discontinuation will be documented in the source and entered into the eCRF. If a subject discontinues from the study (regardless of the cause), all EOS/ET assessments and procedures should be completed. If, however, a subject withdraws consent, no EOS/ET assessments or procedures will be required except for the collection of AE information. This information should be recorded in the source document and entered into the eCRF.

